#### 7.1.5.2. Exacerbation Verification Process

In order to provide an objective assessment of the circumstances linked to the clinical decision that defines asthma exacerbations, in study Part C and Part D each exacerbation recorded in the eCRF by the Investigator or designee will be verified using data from the eDiary to confirm that the exacerbation was associated with changes in peak flow, rescue medication use, nocturnal awakening due to asthma symptoms requiring rescue medication use or symptoms. In the case that an exacerbation is regarded as not associated with deterioration in at least one of these objective eDiary parameters, the investigator will be asked to provide an explanation to support the decision for defining the event as a clinically significant exacerbation. In those circumstances where the event cannot be supported by any objective assessment, the case will not be included as a clinically significant exacerbation but will be included as an investigator defined exacerbation. This verification process will be overseen by GSK clinical staff to ensure consistency. This is the same process as employed in previous Phase III mepolizumab severe asthma studies (MEA112997, MEA115588, MEA115575). This verification process is described in detail within Section 11.9.

## 7.2. Secondary Efficacy Analyses

### 7.2.1. Population of Interest

The population of interest is represented by the randomization inclusion/exclusion criteria of the study and therefore the secondary efficacy analyses will be based on the Intent-to-Treat (ITT) [Part C] population, unless otherwise specified.

### 7.2.2. Statistical Analyses / Methods

Details of the planned displays are provided in [Appendix 11](#): List of Data Displays and will be based on GSK data standards and statistical principles.

#### 7.2.2.1. Statistical Methodology Specification

Endpoint / Variables

 
Ratio to baseline in blood eosinophil count at weeks 12, 24, 36 and 52 (ADaM Dataset: ADLB)
 
See Section 5.2 for further details regarding baseline and change from baseline derivations.
 
See Section 11.6.3 for additional details regarding handling blood eosinophil data.
 

Summary Measure

 
Mean treatment difference at weeks 12, 24, 36 and 52 (Exit Visit/C14)
 

Strategy for Intercurrent (Post-Randomization) Events

 
A hypothetical estimand strategy will be applied in the handling of the intercurrent event of discontinuation of double-blind treatment. The treatment effect therefore refers to the outcome if all patients had continued to take double-blind treatment.
 
Only the On-treatment (Part C) period will be used in the analysis and subjects will be analysed according to the treatment received for more than 50% of injections within Part C (see Section 5.1).
 
All subjects will be considered on-treatment from their first dose of double-blind treatment at visit C1. Subjects who complete Part C will be considered on-treatment up to their Week 52 (Exit Visit/C14) visit date. Subjects who discontinued double-blind treatment will be considered on-treatment until the time of treatment discontinuation. 
 
Blood Eosinophils: see On-treatment (Part C) definition within Section 11.4.3
 
 
 

Model Specification

 
Endpoint will be analysed using a mixed model repeated measures (MMRM) model
 
A log transformation will be applied to blood eosinophil count data prior to analysis.
 
Terms fitted in the MMRM model will include: 
 
Fixed Categorical Covariates: Treatment, Region, Baseline maintenance OCS use [Visit C1], Visit, Visit * Treatment Interaction
 
Fixed Continuous Covariates: Baseline, Exacerbations in the year prior to randomization [Visit C1] (as an ordinal variable), Visit * Baseline
 
Repeated: Visit
 
 
 
See Section 5.4.1 for further details around model covariates.
 

Model Checking & Diagnostics

 
The Kenward and Roger method for approximating the denominator degrees of freedom and correcting for bias in the estimated variance-covariance of the fixed effects will be used (DDMF=KR).
 
An unstructured covariance structure for the R matrix will be used by specifying 'TYPE=UN' on the REPEATED line.
 
In the event that this model fails to converge, the list of covariates may be adjusted and/or reduced.
 
Distributional assumptions underlying the model used for analysis will be examined by obtaining a normal probability plot of the residuals and a plot of the residuals versus the fitted values (i.e. checking
 

the normality assumption and constant variance assumption of the model respectively) to gain confidence that the model assumptions are reasonable.
 
 
• If there are important departures from the distributional assumptions, transformations of covariates may be considered or alternative models may be explored as supportive analysis.
 

Model Results Presentation

 
• The estimated means for each treatment group will be calculated from the model using the observed marginal distributions of the sample covariates (OM option in LSMEANS statement).
 
• Adjusted absolute means and mean changes from baseline will be presented for each treatment by visit with corresponding standard errors of means on the loge scale. The estimated treatment ratios (Mepolizumab/Placebo) will also be presented at each visit with the corresponding 95% confidence intervals and p-values.
 
• Plots of LS means ratio to baseline in blood eosinophil count and 95% confidence intervals from the model will be generated for each treatment by visit.
 

Endpoint / Variables

 
• Time to a decrease in asthma control, defined as an increase from baseline in Asthma Control Questionnaire-5 (ACQ-5) score of <math>\geq 0.5</math> units (ADaM Dataset: ADTTE)
 
• Time to first exacerbation requiring hospitalization or ED visit (ADaM Dataset: ADTTE)
 


 
• Time to first event within Part C will be derived relative to the date of first dose of double-blind treatment [see Section 11.6.1, Part C study day].
 
• See Section 5.2 for further details regarding baseline and change from baseline derivations.
 
• See Section 11.6.3 for details of the ACQ-5 questionnaire and Section 11.3.5 regarding visit windowing.
 
• For consistency, exacerbations separated by less than 7 days will be treated as a continuation of the same exacerbation (see Section 11.6.3).
 
• See Section 11.7.2.1 for details on handling missing/partial dates.
 

Summary Measure

 
• The hazard ratio (Mepolizumab 100mg SC / Placebo) will be the summary measure used for the treatment comparison.
 

Strategy for Intercurrent (Post-Randomization) Events

 
• A hypothetical estimand strategy will be applied in the handling of the intercurrent event of discontinuation of double-blind treatment. The treatment effect therefore refers to the outcome if all patients had continued to take double-blind treatment.
 
• Only the On-treatment (Part C) period will be used in the analysis and subjects will be analysed according to the treatment received for more than 50% of injections within Part C (see Section 5.1).
 
• All subjects will be considered to be at risk from their first dose of double-blind treatment at visit C1. Subjects who complete Part C will be considered to be at risk up to their Week 52 (Exit Visit/C14) visit date. Subjects who discontinued double-blind treatment prior to experiencing an event will be censored at the time of treatment discontinuation.             
 
○ Questionnaires: see On-treatment (Part C) definition within Section 11.4.3
 
○ Exacerbations: see On-treatment (Part C) definition within Section 11.4.2
 
 
 

Model Specification

 
• See Primary Efficacy Statistical Analysis, Section 7.1.5.1
 

Model Checking & Diagnostics

 
• See Primary Efficacy Statistical Analysis, Section 7.1.5.1
 

Model Results Presentation

 
• See Primary Efficacy Statistical Analysis, Section 7.1.5.1
 

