8.3.2.1.1. Guideline for Assessing Multiple Exacerbations

Exacerbations which are separated by less than 7 days will be treated as a continuation of the same exacerbation.

8.3.2.2. eDiary Reporting, Worsening of Asthma and Alerts: Part B, C and D

Subjects should be instructed to bring their eDiary to each Clinic Visit in Part B, Part C and Part D.

The subject will be asked to record the following parameters **daily** in the eDiary from Visit B1 until the completion of Part C or Part D:

- Morning peak flow (best of three), before rescue medication usage (L/min).
- Asthma symptom score over the previous 24-hours using a 6-point scale ([Appendix 7](#))
- Occasions of rescue medication usage over the previous 24-hours
- Frequency of awakening due to asthma symptoms requiring rescue medication use

8.3.2.2.1. eDiary Alerts Indicating Worsening of Asthma

For safety the following alerts, indicative of worsening asthma, will be programmed into the eDiary with instructions to contact the investigator if any of the alert criteria are met.

NOTE: An alert in itself will not qualify as a clinically significant exacerbation:

- Decrease in morning PEF $\geq 30\%$ on at least two of three consecutive days, compared with baseline (last 7 days of run-in Part B)
- A symptom score of 5 for at least two of three consecutive days
- An increase of $\geq 50\%$ in occasions of rescue medication on at least two of three consecutive days, compared with the average use for the previous week.
- Awakening due to asthma symptoms requiring rescue medication use for at least two of three consecutive nights.

Sites should review subject data weekly during Part C through a study specific web portal, and contact subjects for follow-up as appropriate. Additionally, eDiary data will be reviewed at each clinic visit in Parts C and D by the site staff throughout the treatment period to confirm an association between any exacerbation event and eDiary data.

8.3.2.2.2. eDiary Daily Entry: Missed Days of Work or School

Subjects who work for pay or go to school on a regular basis will record in the eDiary any full and part days of missed work or school due to asthma.

8.3.2.2.3. eDiary Weekly Entry: Asthma Control Questionnaire-5 (ACQ-5)

Subjects in Part B, Part C and Part D should complete the ACQ-5 on their eDiary once weekly.

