#### 7.3.2.1. Statistical Methodology Specification

Endpoint / Variables

 
• Time to first exacerbation requiring hospitalization (ADaM Dataset: ADTTE)
 
• Time to worsening of asthma (subjects meeting at least 2 of the following 4 criteria for worsening of asthma for at least 2 consecutive days) (ADaM Dataset: ADTTE):               
 
○ AM PEF: Decrease in AM PEF <math>\geq 30\%</math> compared with Part C baseline
 
○ Rescue Medication Use: An increase of <math>\geq 50\%</math> in rescue medication compared with the average use for the previous week
 
○ Night time awakenings requiring rescue medication: Awakening due to asthma symptoms requiring rescue medication
 
○ Symptoms: An asthma symptom score of 5
 
 
 

 
• Time to first event within Part C will be derived relative to the date of first dose of double-blind treatment [see Section 11.6.1, Part C study day].
 
• For consistency, exacerbations separated by less than 7 days will be treated as a continuation of the same exacerbation (see Section 11.6.3).
 
• See Section 5.2 for further details regarding baseline and change from baseline derivations.
 
• See Section 11.6.3 for details regarding eDiary data and Section 11.3.5 regarding visit windowing.
 
• In the analysis of Time to worsening of asthma only non-missing measurements indicative of asthma worsening (per above endpoint definition) will be considered as an event. Intermediate missing responses in a subject's eDiary data will be assumed to be missing at random, and will not be considered to indicate a worsening of their asthma.
 
• See Section 11.7.2 for further details on handling missing/partial data.
 

Summary Measure

 
• The hazard ratio (Mepolizumab 100mg SC / Placebo) will be the summary measure used for the treatment comparison.
 

Strategy for Intercurrent (Post-Randomization) Events

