
 
• A hypothetical estimand strategy will be applied in the handling of the intercurrent event of discontinuation of double-blind treatment. The treatment effect therefore refers to the outcome if all patients had continued to take double-blind treatment.
 
• Only the On-treatment (Part C) period will be used in the analysis and subjects will be analysed according to the treatment received for more than 50% of injections within Part C (see Section 5.1).
 
• All subjects will be considered to be at risk from their first dose of double-blind treatment at visit C1. Subjects who complete Part C will be considered to be at risk up to their Week 52 (Exit Visit/C14) visit date. Subjects who discontinued double-blind treatment prior to experiencing an event will be censored at the time of treatment discontinuation.               
 
○ Exacerbations: see On-treatment (Part C) definition within Section 11.4.2
 
○ eDiary data: see On-treatment (Part C) definition within Section 11.4.3.
 
 
 

Model Specification

 
See Primary Efficacy Statistical Analysis, Section 7.1.5.1
 

Model Checking & Diagnostics

 
See Primary Efficacy Statistical Analysis, Section 7.1.5.1
 

Model Results Presentation

 
See Primary Efficacy Statistical Analysis, Section 7.1.5.1
 

Endpoint / Variables

 
Mean change from baseline in clinic pre-bronchodilator FEV1 at weeks 12, 24, 36, 52
 
Mean change from baseline in clinic post-bronchodilator FEV1 at weeks 12, 24, 36, 52 (ADaM Dataset: ADPFT)
 
Mean change from baseline in ACQ-5 score (ADaM Dataset: ADACQ5)
 
Mean change from baseline in SGRQ Total score at week 12, 24, 36 and 52
 
Mean change from baseline in SGRQ Symptom Domain score at week 12, 24, 36 and 52
 
Mean change from baseline in SGRQ Activity Domain score at week 12, 24, 36 and 52
 
Mean change from baseline in SGRQ Impacts Domain score at week 12, 24, 36 and 52 (ADaM Dataset: ADSGRQ)
 

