**11.4.3. Treatment Phases (Visit Based Efficacy and Safety Data)**

Visit based efficacy data, safety data and eDiary data will be classified into treatment phases according to the time of occurrence/assessment relative to the dates of the study treatment and/or the participation of subjects within specific study parts (as dictated by attendance at specific visits) as shown in the table below:

Treatment Phase	Definition
Pre-treatment	Date & time $\leq$ First dose of open-label mepolizumab
On-treatment (Parts A/B)	Subjects who are randomized and receive double-blind treatment: First dose of open-label mepolizumab < Date & time $\leq$ First dose of double-blind treatment Subjects who are not randomized: First dose of open-label mepolizumab < Date & time $\leq$ Earliest of (1) Last dose of open-label mepolizumab + 28 days or (2) Early Withdrawal visit date 
Post-treatment (Parts A/B)	Subjects who are not randomized: Date & time > Earliest of (1) Last dose of open-label mepolizumab + 28 days or (2) Early Withdrawal visit date 
On-treatment (Part C)	Subjects completing study Part C: First dose of double-blind treatment < Date & time $\leq$ C14 (Exit Visit) visit date Subjects discontinuing study treatment/withdrawing early from within Part C: First dose of double-blind treatment < Date & time $\leq$ Earliest of (1) Last dose of double-blind treatment + 28 days or (2) Early Withdrawal / IP Discontinuation visit date Subjects who switch to study Part D: First dose of double-blind treatment < Date & time $\leq$ First dose of open-label mepolizumab within Part D
Post-treatment (Part C)	Subjects completing study Part C: Date & time > C14 (Exit Visit) visit date Subjects discontinuing study treatment/withdrawing early from within Part C: Date & time > Earliest of (1) Last dose of double-blind treatment + 28 days or (2) Early Withdrawal / IP Discontinuation visit date
On-treatment (Part D)	Subjects completing study Part D: First dose of open-label mepolizumab within Part D < Date & time $\leq$ D14 (Exit Visit) visit date Subjects discontinuing study treatment/withdrawing early from within Part D: First dose of open-label mepolizumab within Part D < Date & time $\leq$ Earliest of (1) Last dose of open-label mepolizumab within Part D + 28 days or (2) Early Withdrawal / IP Discontinuation visit date

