### 11.7.2. Handling of Missing Data

Element	Reporting Detail
General	
 
• Missing data occurs when any requested data is not provided, leading to blank fields on the collection instrument: 
 
○ These data will be indicated by the use of a “blank” in subject listing displays. Unless all data for a specific visit are missing in which case the data is excluded from the listing.
 
○ Answers such as “Not applicable” and “Not evaluable” are not considered to be missing data and should be displayed as reported.
 
 
 
• Results which are found to be below the limit of quantification (BLQ) are not missing data and will be included in all displays. See Section 11.6 for the handling of this data.
 
• If a blood eosinophil count of zero is reported, it will be imputed with half of the lowest possible blood eosinophil count, where applicable, prior to log transforming the data (Note: this imputation has typically been <math>0.5 * 0.01 \text{ } 10^9/\text{L} = 0.005 \text{ } 10^9/\text{L}</math> for previous mepolizumab studies).
 
• The ACQ-5 score will be considered as missing if 2 or more items of the questionnaire are not completed at a visit. ACQ-5 Responder/Non-responder category will be missing if the ACQ-5 score is missing.
 

Element	Reporting Detail
	
 
Scoring of each domain of the SGRQ (Symptoms, Activity, Impacts) and the Total score are described in the St George's Respiratory Questionnaire Manual (Version 2.3), including possible missing scores following missed items. SGRQ Responder/Non-responder category will be missing if the Total SGRQ score is missing.
 
Missing values will not be imputed for any of the other endpoints.
 
When handling eDiary parameters (see Section 11.6.3) missing responses in each patient's daily diary will be assumed to be missing at random. As a result only non-missing eDiary measurements will be summarised in 4-weekly windows (see Section 11.3.5) and only non-missing eDiary measurements will be considered in the exploratory endpoint of Time to worsening of asthma which is defined according to the four measured eDiary parameters (see Section 7.3.2.1).
 

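### Time to ACQ-5 worsening (secondary) and time to worsening of asthma (exploratory) count on-treatment time after the last eDiary entry as event-free

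*SAP*

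**What the plan says.** **Risk period.** SAP 7.2.2.1, for time to a decrease in asthma control, states: "Subjects who complete Part C will be considered to be at risk up to their Week 52 (Exit Visit/C14) visit date". SAP 7.3.2.1 repeats this for time to worsening of asthma and gives the only other rule: "Subjects who discontinued double-blind treatment prior to experiencing an event will be censored at the time of treatment discontinuation". Section 7.2.2.1 has the same censoring rule. Both sections refer to the on-treatment phase in SAP 11.4.3, which is set "relative to the dates of the study treatment and/or the participation of subjects within specific study parts", that is, by dose and visit dates. No section ends risk time at the last score or diary day.

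**Source of the events.** Protocol 8.3.2.2.3 sets the ACQ-5 schedule: "Subjects in Part B, Part C and Part D should complete the ACQ-5 on their eDiary once weekly". The paper ACQ-5 is for Part A only (Protocol 8.3.2.5). The four criteria for worsening of asthma come from the daily eDiary (Protocol 8.3.2.2). Completion below 80% leads to re-education, not to stopping treatment (Protocol 8.3.2.2.4).

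**Missing data.** SAP 11.7.2 says of daily data that "missing responses in each patient's daily diary will be assumed to be missing at random", and that "only non-missing eDiary measurements will be considered in the exploratory endpoint of Time to worsening of asthma". SAP 7.3.2.1 says intermediate gaps "will be assumed to be missing at random, and will not be considered to indicate a worsening of their asthma". For endpoints without a rule of their own, 11.7.2 says: "Missing values will not be imputed for any of the other endpoints".

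**The concern.** The at-risk rule is the one used for the primary endpoint (SAP 7.1.4). It suits exacerbations, which are reviewed at every clinic visit and recorded in the eCRF, so a subject attending visits really is under observation. It does not suit an outcome that exists only when the subject makes an entry. A subject who stops scoring at Week 20 but is injected to Week 48 and attends the Exit Visit adds about 32 weeks in which no event could be recorded, all counted as event-free.

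Two results are at stake. Kaplan-Meier incidence is a planned output for both endpoints (SAP Figures 2.9 and 2.17), and it would be too low. The hazard ratio would favour whichever arm stops making entries more. For the exploratory endpoint there is also a conflict within the SAP: if missing daily responses are missing at random, unobserved time should leave the risk set, not stay in it as time without an event.

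**Working it through.** **The plan's own figure.** None exists for these two endpoints. The power section concerns the primary endpoint and reproduces: 150 × (0.605 + 0.40) × 0.8 = 120.6 events, and √(120.6/4) × |ln 0.55| − 1.96 = 1.32, which is 90.7% power against the stated 90%. This does not bear on the point, but it supplies event proportions to borrow.

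**Assumptions not in the documents.** These are the ACQ-5 and worsening event rates, the withdrawal rate, and the share *p* in each arm who stop making entries by Week 52 while still treated. Event and stopping times are exponential. Stopping is independent of the event unless stated.

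**Incidence under the SAP rule.** Let λ be the yearly event hazard and μ = −ln(1 − p). An event is seen only if it precedes stopping, so the Week 52 Kaplan-Meier incidence is

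λ/(λ + μ) × [1 − e^−(λ+μ)].

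Take the primary endpoint's proportions (60.5% and 40%; hazard ratio 0.511/0.929 = 0.55) and p = 20% in both arms, so μ = 0.223.

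- Placebo: λ = −ln 0.395 = 0.929. 0.929/1.152 × (1 − 0.395 × 0.80) = 0.806 × 0.684 = 55.2%, against a true 60.5%.
- Mepolizumab: λ = −ln 0.60 = 0.511. 0.511/0.734 × (1 − 0.60 × 0.80) = 0.696 × 0.520 = 36.2%, against a true 40%.

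Simulation with weekly scores (150,000 per arm) gave 55.1% and 36.1%. With censoring at the last score it gave 60.6% and 40.0%.

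**Hazard ratio.** Simulated with event hazards of 1.2 and 0.72 per year (true ratio 0.60), withdrawal of 0.32 per year and at least 200,000 subjects per arm:

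| Stopping, placebo / mepolizumab | SAP rule | Censored at last entry |
|---|---|---|
| 10% / 10% to 30% / 30% | 0.60 to 0.62 | about 0.60 |
| 5% / 2% | 0.61 | about 0.60 |
| 10% / 5% | 0.62 | about 0.60 |
| 25% / 10% | 0.67 | about 0.60 |
| 10% / 25% | about 0.56 | about 0.60 |

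Over the equal-stopping rows (10%, 20%, 30%), Week 52 incidence falls from 0.70 to 0.67, 0.64 and 0.61 on placebo, and from 0.51 to 0.49, 0.47 and 0.44 on mepolizumab.

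**No true effect.** Stopping of 25% / 10% gives a hazard ratio of 1.09 to 1.10 under the SAP rule; reversed, it gives 0.91. With a 60.5% event proportion, 30% / 10% gives 1.14 and 10% / 30% gives 0.87. Censoring at the last entry gives about 1.00 throughout.

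**Informative stopping.** Suppose 25% of placebo and 10% of mepolizumab subjects stop one week before their event. The hazard ratio (true 0.60) is 0.81 under the SAP rule and about 0.72 with censoring at the last entry.

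**Precision, for scale.** Expected events per arm are 150 × λ/(λ + 0.32) × [1 − e^−(λ+0.32)], which is 92.5 on placebo and 67.1 on mepolizumab. The standard error of the log hazard ratio is about 2/√159.6 = 0.158, so a 95% interval around 0.60 is roughly 0.44 to 0.82.

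**The case against.** **The SAP is silent, not explicit.** The at-risk sentence sits under intercurrent events, where treatment discontinuation is the only event named, and 7.3.2.1 speaks only of intermediate gaps. A dataset specification outside these documents might end risk at the last score. This stands as a limit on predicting what will be programmed. It does not rescue the text, which followed as written keeps a treated non-scorer at risk.

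**Safeguards exist.** Randomization requires recent diary completion, sites review entries weekly in Part C, discontinuers and Part D switchers are already censored, and after a gap a later score can still register a lasting worsening. These points narrow the problem to permanent stopping while on treatment. No post-baseline score at all should be rare.

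**The effect may be small.** Equal stopping, or small differences, moves the hazard ratio by about 0.02 or less, well inside the confidence interval. If the placebo arm stops more because control is lost, the bias is towards 1 and so conservative for superiority. Both points are fair. They do not touch the understated incidence or the opposite direction.

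**Two stronger readings are not supported.** A reader might infer that the missing-at-random text contradicts the ACQ-5 analysis. That text covers daily diary data, the 4-weekly summaries and time to worsening of asthma; the SAP says nothing comparable for weekly ACQ-5 scores. A reader might also see a contradiction with the ACQ-5 proportion endpoint, which counts a missing score as worsened. That endpoint declares a composite strategy and this one a hypothetical strategy, so different handling is not an inconsistency.

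**Conclusion.** The point holds for one secondary and one exploratory endpoint. As written, the SAP counts on-treatment time after the last eDiary entry as event-free, although no event can then be recorded. Incidence is understated in both arms, by about 5 points on placebo and 4 on mepolizumab at 20% stopping. The hazard ratio is biased only to the extent that stopping differs by arm: from 0.60 to about 0.67 or 0.56 at 25% versus 10%. These sizes rest on assumed event and stopping rates; the documents provide neither, and neither the presence nor the direction of a difference is known. The conflict with the missing-at-random assumption applies to the exploratory endpoint only.

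A reader might infer that the primary result is at risk. It is not: exacerbations are recorded in the eCRF, and SAP 11.9 allows other objective evidence to support an event when the diary does not. The secondary endpoint has no multiplicity adjustment (SAP 5.5), so this is a correction worth making rather than a threat to the trial's main conclusion. Nor does censoring at the last entry cure everything: it removes the bias only when stopping is non-informative.

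**What to change.** Before unblinding, add one sentence to each of SAP 7.2.2.1 (ACQ-5) and 7.3.2.1 (time to worsening of asthma):

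- Censor event-free subjects at the earlier of the current on-treatment end and the last non-missing ACQ-5 score, or the last eDiary day on which the worsening criteria could be evaluated.
- Censor subjects with no post-baseline entry at Day 1.

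Then:

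- Report eDiary and ACQ-5 completion, and the number censored at Day 1, by arm. Subjects censored at Day 1 contribute nothing to the comparison, so the reader should see how many there are.
- Keep the current at-risk rule as a sensitivity analysis, since stopping may be informative.

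The cost is two sentences, one line in the time-to-event dataset derivation, one completion summary and one repeat run per endpoint. No new data are needed.
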